9.9. Subject Registry Exit

A subject may be exited from the investigation for the following reasons:

- **Subject completes all investigation or safety follow-up visits**
- **Subject withdraws consent**
- **Subject death**

- **Index valve explant**
- **Investigator withdraws the subject**
- **Subject failed INTUITY ELITE attempt (after the 30 days FU phone visit)**
- **Conversion from MIS to full sternotomy approach (after the 30 days FU phone visit)**

9.9.1. SUBJECT REGISTRY COMPLETION

Registry subjects complete and exit from the registry when no additional follow-up visits, procedures, or data collection are required. Once participation is completed subjects will then continue to be followed by their primary health care provider per standard medical practice.

9.9.2. SUBJECT VOLUNTARY WITHDRAWAL

Although all subjects are informed of their right to withdraw from the registry at any time, it is anticipated that such withdrawals will be infrequent. All measures should be taken by the Investigator and their staff to encourage patients to be available for required follow-up visit by phone at 30 days and return for required follow-up visit at 6 months post-procedure. The registry objective may be jeopardized if large numbers of patients are lost to follow-up.

All patients are expected to continue in the registry until Edwards notifies the Investigator in writing that further follow-up is no longer required, except in the event of death or upon the subject's written request for early withdrawal from the registry. A copy of the withdrawal request should be forwarded to sponsor via the monitor for documentation.

9.10. Subject death

In the event of subject death, every effort should be made to obtain a copy of the autopsy report, death certificate and/or death summary, if applicable. Information on the cause of death and its relationship to the registry device will be evaluated and reported by the Investigator.

9.11. Index Valve Explant

Explant is defined as a re-intervention resulting in removal of the implanted valve after the patient left the operating room with an implanted valve, after the index procedure

If a registry subject requires explant of an EDWARDS INTUITY Elite Valve due to a complication, data will be documented on the Device Explant CRF and Adverse Event CRF forms.

After the EDWARDS INTUITY Elite Valve has been explanted, the subject should be followed for safety for 30-days post-explant or until the complication related to the explant is resolved. Once subjects have completed safety follow-up, they should be exited from the registry.

Every effort should be made to return the explanted EDWARDS INTUITY Elite Valve, at autopsy or explantation to Edwards Lifesciences. The explanted valve should be placed in a container with a suitable histological fixative such as 10% formalin or 2% glutaraldehyde immediately after excision. Refrigeration is not necessary under these circumstances. The Investigator should contact the local clinical specialist for further instructions for return of recovered bioprostheses.

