6. REGISTRY OBJECTIVES

Primary Objective:

- To describe procedural time (Cross Clamp Time) and to compare the Cross Clamp Time collected with EDWARDS INTUITY Elite in this registry to the largest published dataset with conventional valves within the MIS setting (Merck et al ²¹). The published dataset will be used as a control group.

Secondary Objectives:

- To describe short term (30 days) and long term (6 months) clinical safety
- To assess and compare hemodynamic data with EDWARDS INTUITY Elite to a conventional valve at discharge and at 6 months post AVR
- To assess Quality of Life at baseline, and at 6 months post AVR
- To assess NYHA functional class at baseline, discharge and at 6 months post AVR
- To assess Fitness for hospital discharge

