9.8. Follow-up Visits Registry Procedures

9.8.1. FOLLOW-UP VISIT WINDOWS

Post-procedure clinical evaluation will be performed on all enrolled subjects at 30-days and 6-months post-implant date. Follow-up at 30 days- will be conducted by phone. All follow-up data will be documented on the CRF.

Patient assessments will be done according to the sites standard of care.

It is important that the follow-up visit schedule is maintained as closely as possible for all subjects. Edward's recognizes that subjects may not be able to return for all scheduled visits at precisely the date required, and therefore, an acceptable window of time for the 30 day follow-up period is described in Table 1. Registry visits should be scheduled as close to the earliest portion of the window for the follow-up period so that cancellations and visit rescheduling can still be conducted within the required time period.

TABLE 1. SCHEDULED FOLLOW-UP VISIT DAYS AND APPLICABLE VISIT WINDOWS

Visit	Visit Window days	Timing from Implant (Day 0)
Screening		Day -30 to Day -1
Discharge		Post-op - Day of Discharge
POD 30	+/- 7	Day 23 to Day 37
POD 180 (if applicable)	+/- 45	Day 135 to Day 225

Protocol required registry follow-up not performed will be considered a missed visit.

9.8.2. 30 DAYS FOLLOW-UP VISIT: REQUIRED PROCEDURES AND EVALUATIONS

The 30 day follow-up visit shall be performed by phone. The clinical evaluation and data requirements for the registry subjects at POD 30:

- Adverse Events: Post-operative procedure or cardiac related events that resulted in medical or surgical intervention; all other serious adverse events per investigators decision using the available adverse event code list will also be collected.
- NYHA classification

9.8.3. 180 DAYS (6 MONTHS) FOLLOW-UP VISIT: REQUIRED PROCEDURES AND EVALUATIONS

The 6 month follow-up visit shall be performed at the investigational site, if applicable. The clinical evaluation and data requirements for the registry subjects at POD 180:

- Adverse Events: Post-operative procedure or cardiac related events that resulted in medical or surgical intervention all other serious adverse events per investigators decision using the available adverse event code list will also be collected.
- Medical examination: HR, BP, NYHA classification, weight
- ECG 12 lead
- Echocardiography data will be collected (if available and CD will be sent to CoreLab)
- Anticoagulation therapy
- Coagulation profile: INR and PT

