12.3. SAFETY DATA

- All cause mortality
 - Study valve-related mortality
- Thromboembolism (Stroke, TIA, and Non cerebral embolism)
- Valve Thrombosis
- Major Bleeding event

- Endocarditis (study valve)
- Structural valve deterioration
- Non Structural valve deterioration
 - Paravalvular Leak minor
 - Paravalvular Leak major
 - Other non SVD
- Hemolysis
- Reoperation
 - Trial valve reoperation
- Study valve explants
- Implant-related new or worsened cardiac conduction disturbance requiring permanent pacemaker implant
- Renal Failure
- Respiratory Failure
- Deep Sternal Wound infection

Early adverse events within 30 days of procedure will be reported as the number of events divided by the number of enrolled subjects. Linearized rates will be used to summarize adverse events for the late (>30 days) post-operative period. The linearized rates will be calculated as the number of late events divided by the total number of late-subject years.

Percentages for the early events and linearized rates for the late events also will be calculated for all other complications observed in the trial.

Actuarial rates based on the method of Kaplan - Meier will be calculated for each of the safety endpoints at thirty days and six months; the number of subjects at risk for death will be reported at each of these intervals.

On top of Implant-related new or worsened cardiac conduction disturbance requiring permanent pacemaker, the counts and percentage of subjects who experience new or worsening cardiac rhythm or conduction disturbances will be calculated at each follow-up visit. The identification of “new and worsening” cardiac rhythm or conduction disturbance will be based on a comparison to the previous visit.

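### Registry exit after valve explant makes the censoring in the six-month safety rates potentially informative, and contradicts the rules that keep all enrolled subjects in follow-up to 6 months

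*Combined protocol and SAP*

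**What the plan says.** **Exit rule.** Section 9.11 sets the follow-up after explant: "the subject should be followed for safety for 30-days post-explant or until the complication related to the explant is resolved". It continues: "Once subjects have completed safety follow-up, they should be exited from the registry". Section 9.9 includes "Index valve explant" in its list of exit reasons.

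**Continuation rules.** Section 9.9.2 reads: "All patients are expected to continue in the registry until Edwards notifies the Investigator in writing that further follow-up is no longer required". The exceptions it allows are death and the subject's own written withdrawal; explant is not among them. Section 9.8.1 reads: "Post-procedure clinical evaluation will be performed on all enrolled subjects at 30-days and 6-months post-implant date". Section 5 likewise schedules every enrolled subject for assessment at 6 months.

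**Objective and analysis.** A secondary objective in Section 6 is "To describe short term (30 days) and long term (6 months) clinical safety". Section 12.3 says that Kaplan-Meier rates "will be calculated for each of the safety endpoints at thirty days and six months", and adds linearized rates (late events over late subject-years) for the period after 30 days. Section 12.1.2 bases all safety summaries on subjects who left the operating room with the registry valve in place after an MIS procedure. Neither Section 12.3 nor Section 12.4 says how an exit because of explant enters these estimates.

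**The concern.** Kaplan-Meier and linearized rates both assume that subjects whose follow-up stops early have the same later risk as those still observed. Here follow-up stops because the device failed and had to be removed, so that assumption is doubtful.

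The outcomes that may be lost belong to the endpoints. Table 2 counts a death related to re-intervention on the operated valve as registry valve-related mortality, and it defines explant as a re-intervention. A death from the later consequences of an explant is therefore a valve-related death by the protocol's own definition, yet it can fall after exit.

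Section 2.2 says the data will support publications and marketing information. Late deaths may be few, so even one missed death could matter. Separately, sites face two incompatible instructions and may apply different ones.

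**Working it through.** The plan gives no explant rate, mortality rate or precision target for six-month safety, so it has no figure of its own to reproduce on this point. Its only power statement concerns cross clamp time, which this rule does not touch.

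**1. Who is affected.** Explant is defined (Section 9.11, Table 2, Appendix C) as removal after the patient has left the operating room with the valve. A subject who left after an MIS procedure meets Section 12.1.2 and stays in the safety cohort after explant.

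**2. Follow-up lost under the 30-day limb.** Days lost before Day 180 = 180 - (explant day + 30).

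| Explant day | Exit day | Days lost |
|---|---|---|
| 15 | 45 | 135 |
| 60 | 90 | 90 |
| 120 | 150 | 30 |
| 150 or later | 180 or later | 0 |

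Every post-operative explant is followed past Day 30 under this limb, so 30-day mortality is not affected.

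**3. Effect on six-month Kaplan-Meier mortality.** From the documents: N = 300 and a 180-day horizon. Assumed, because the documents are silent:
- six-month mortality without explant, m = 2% or 4%;
- share explanted, e = 1%, 2% or 5% (3, 6 or 15 of 300);
- explant on Day 15, 60 or 120;
- a hazard 10 times background in the 30 observed days after explant;
- a hazard r times background after exit, with r = 0.5, 1, 3 or 10.

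The daily background hazard is h = -ln(1 - m)/180. With full follow-up, each day's hazard is the average over explanted and other subjects, weighted by the numbers still at risk. Under the exit rule, only the other subjects contribute after exit. The error is the exit-rule estimate minus the full-follow-up estimate.

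| Hazard ratio after exit, r | Error in six-month mortality (percentage points) |
|---|---|
| 0.5 | +0.00 to +0.07 |
| 1 | 0.00 |
| 3 | -0.01 to -0.27 |
| 10 | -0.03 to -1.09 |

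Example: with m = 2%, e = 2% (6 of 300), explant on Day 15 and r = 3, full follow-up gives 2.12% and the exit rule gives 2.06%. A first-order check agrees. h = 0.0202/180 = 0.000112 per day, and the shift is about e(r - 1)h x days lost = 0.02 x 2 x 0.000112 x 135 = 0.0006, or 0.06 points.

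**4. Rough upper bound.** If every explanted subject died unseen after exit, the shift would be about (explants)/300: 3/300 = 1.0 point, or 6/300 = 2.0 points.

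**5. Consistency of the text.** Sections 9.9 and 9.11 end follow-up after explant. Sections 5, 9.8.1 and 9.9.2 keep the same subject in until 6 months or until the sponsor's notice. No passage says which prevails.

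**The case against.** **The rule need not stop at 30 days.** Section 9.11 offers resolution of the complication as an alternative, and Section 11.1 follows adverse events until they are resolved or explained. A subject dying from the consequences of a failed valve is the one most likely to have an unresolved complication and so still be under observation. This stands: a reader might infer that every explanted subject is lost at 30 days, and the text does not say so. It also does not say which limb governs, and resolution could come sooner as well as later.

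**The direction is not proven.** A reader might infer that six-month mortality is certainly biased low. That requires a higher hazard after exit than among subjects still followed. This is plausible after a second valve operation, but the documents give no rate. The error vanishes at equal hazard and reverses at a lower one.

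**A large relative effect is not supported.** Four late deaths in 300, 6 to 9 explants and 10 to 20% mortality after exit would suggest late mortality understated by 10 to 30%. All those inputs are undocumented. They imply a hazard after exit of about 8 times background for 10% over 150 days (0.105/0.0134 = 7.8), and about 23 times for 20% over 110 days ((0.223/110)/(0.0134/150) = 22.7). Dividing by 300 less the explants also removes those subjects from the whole period, which Kaplan-Meier does not do.

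**The failure itself is visible.** Explant and valve reoperation are reported endpoints, and deaths during the follow-up after explant count. The objective is secondary and descriptive, and the 6-month visit is qualified as if applicable for everyone. All of this limits the importance, but none of it resolves the contradiction or recovers outcomes after exit.

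**Conclusion.** The point holds as a design weakness and an internal contradiction. If Sections 9.9 and 9.11 prevail, follow-up ends early for subjects whose device failed, and for explants before about Day 150 under the 30-day limb, later deaths and other safety events may go unrecorded. Six-month mortality is then probably understated, by an amount the documents do not allow to be estimated. It is likely small in absolute terms if explants are few: 0.01 to 0.27 points at an assumed hazard ratio of 3, and zero at a ratio of 1. The direction rests on the assumption of higher risk after exit. The primary endpoint is unaffected, as is 30-day mortality under the 30-day limb. The change is worth making because the lost outcomes cannot be recovered at analysis and collecting them costs little.

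**What to change.** - **Reconcile Sections 5, 9.8.1, 9.9, 9.9.2 and 9.11** so that a subject whose registry valve is explanted stays in the registry for vital status and non-valve safety endpoints through the POD 180 contact, by phone if needed. Say how the two limbs of the Section 9.11 follow-up rule combine. This concerns data collection, not clinical care.
- **State in Section 12.3** that only endpoints needing the registry valve in place, such as structural valve deterioration, valve thrombosis and paravalvular leak, are censored at explant. All-cause and valve-related mortality are not.
- **Report the number of explant exits** with the six-month rates. If any subject still lacks Day 180 status, show the bound of (such subjects)/N beside the estimate.

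Cost: protocol wording, one extra contact for a few subjects, and possibly slightly less favourable six-month rates. The consent form must be checked. A reader might assume it already covers this contact, but the sample form is not in the text available for review, and inclusion criterion 6 in Section 8.2 refers only to follow-up as specified in the protocol and consent.

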9.11.1. EDWARDS INTUITY ELITE VALVE INTRA-OPERATIVE REMOVAL

Intra-operative removal is the removal of the registry valve before the index EDWARDS INTUITY Elite Valve System procedure was completed (the patient was not transported from the operating room after the index implant procedure). The subject will be followed for 30 days post the surgical procedure (including discharge and 30 days FU visits)

During the index operation, should removal of the registry valve be required after the frame was expanded, the surgeon should use a scalpel to cut the retaining sutures on the valve holder to enable removal of the valve holder and complete delivery system. Next, insert a nerve hook through the outflow aspect of the registry valve. The surgeon should engage the expanded frame with the nerve hook and gently pull the frame inward. Then, surgeon should disengage the collapsed portion of the frame and engage the expanded frame at another location, gently pulling the frame inwards. The expanded frame should be engaged and collapsed at least at 3 radial locations. Once the frame is collapsed, the operator shall cut the nadir sutures and remove the bioprosthetic with forceps.

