9.6. Operative Procedures

In the operating room, the intra-operative and eligibility exclusion criteria will be assessed by careful examination of the valve anatomy, valve condition and associated structures.

All data collected on the operative procedure will be documented into the eCRF. Subjects will be prepped for a minimally invasive surgical approach used for isolated aortic valve replacement. Minimal invasive surgery (MIS) is defined as a non-full sternotomy approach such as partial hemi-sternotomy and right anterior thoracotomy.

A detailed description of device preparation and use is provided in the Instructions for Use (See Appendix I for both the EDWARDS INTUITY Elite Valve, Model 8300AB and EDWARDS INTUITY Elite Delivery System, Model 8300DB. Investigators will be advised of the EDWARDS INTUITY Elite Valve System device preparation and use techniques per the Instructions for Use (IFU) during the mandatory training program.

The procedure will be considered a technical success if the subject leaves the Operating Room with the EDWARDS INTUITY Elite valve in place.

The procedure will be considered a procedural success in case of technical success followed by the absence of adverse events requiring device reoperation, requiring implantation of permanent pacemaker (with baseline sinus rhythm and no other conduction issues), or subject death, within discharge or 10 days post index procedure whichever comes first.

The number of attempts (maximum 2) and final outcome of each EDWARDS INTUITY Elite Valve placement attempt shall be documented on the Device Performance form in CRF.

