9.6.1. OPERATIVE DATA COLLECTION REQUIREMENTS

The sponsor will provide a worksheet to note the various activities throughout the procedure. These data will be transferred to the procedure CRF.

- Intra-operative eligibility criteria (Aortic valve anatomy, Aortic valve condition (annulus/leaflets), condition of surrounding structures)
- Procedure Date
- Procedure Time: Cross Clamp Time (XCT), Cardiopulmonary Bypass Time(CPB)
- Surgical Approach (partial hemi-sternotomy or right anterior thoracotomy) and whether conversion to full sternotomy was required
- Implant Data: Valve Model, Serial Number and Valve Size
- Delivery System: Model, Serial Number and Size
- Suture Technique
- Implant Attempts
- Technical Success
- Final Device Implanted
- Implant Evaluation
- Intraoperative Adverse Events/ Complications
- Ventilation time

The subjects for which an EDWARDS INTUTY Elite Valve is attempted, but not successfully implanted or the minimally invasive surgical approach is converted to a full sternotomy after the valve implant procedure is initiated will be followed for 30 days post valve implant procedure. The discharge visit, 30 days FU Phone visit and adverse events if applicable will be collected. The subject will be exited from the registry at after the 30 days FU Phone visit or not until all adverse events associated with the above scenarios' are resolved. Once subjects have completed safety follow-up, they should be exited from the registry.

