12.1.2. PER PROTOCOL COHORT

The per protocol cohort will consist of all enrolled patients that leave the operating room with the registry valve in place and had an AVR MIS surgery procedure. All summaries of the safety endpoints and other safety data will be based on the per protocol cohort. The summaries of the primary, secondary and patient related endpoints will also be based on the per protocol cohort.

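### Section 9.11.1 gives 30-day follow-up after any intra-operative valve removal, with no exception for a successful second registry valve, which conflicts with 9.6.1 and 9.8.1

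*Combined protocol and SAP*

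**What the plan says.** All references are to the combined protocol and SAP.

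- **Attempts (9.6).** "The number of attempts (maximum 2) and final outcome of each EDWARDS INTUITY Elite Valve placement attempt shall be documented". Success is judged on the final state: "The procedure will be considered a technical success if the subject leaves the Operating Room with the EDWARDS INTUITY Elite valve in place". First attempt success rate is a separate secondary endpoint (7.2).
- **Removal in the operating room (9.11.1).** "Intra-operative removal is the removal of the registry valve before the index EDWARDS INTUITY Elite Valve System procedure was completed". The follow-up rule comes straight after this definition: "The subject will be followed for 30 days post the surgical procedure (including discharge and 30 days FU visits".
- **Who gets 30-day follow-up (9.6.1).** "The subjects for which an EDWARDS INTUTY Elite Valve is attempted, but not successfully implanted", together with subjects converted to full sternotomy once the implant procedure has begun. These subjects leave the registry after the 30-day call, or later if related adverse events are still open.
- **Scheduled follow-up (9.8.1).** Every enrolled subject is to be evaluated at 30 days and at 6 months. Table 1 marks the 6-month visit as held where applicable.
- **Exit reasons (9.9).** One is "Subject failed INTUITY ELITE attempt (after the 30 days FU phone visit". The next is conversion to full sternotomy, at the same time point.
- **Analysis set (12.1.2).** The per protocol cohort is "all enrolled patients that leave the operating room with the registry valve in place and had an AVR MIS surgery procedure". The number of attempts is not a criterion.
- **Analysis (12.3, 12.4).** Late events are summarized as linearized rates, and Kaplan-Meier estimates are given at thirty days and six months. Effectiveness summaries use available data without imputation.

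**The concern.** Consider a subject whose first registry valve is removed in the operating room and whose second is implanted through MIS. The two-attempt allowance and the first-attempt endpoint show that the plan foresees this case. The subject is a technical success and belongs to the per protocol cohort. Sections 9.8.1 and 9.6.1 lead to 6-month follow-up; 9.11.1, taken at its word, provides for 30 days only.

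Up to 30 centers could resolve this differently. Where a site follows 9.11.1, a subject who has the study valve and is counted in the analysis cohort has no 6-month gradients, orifice area, regurgitation grade, NYHA class or quality-of-life change. In the late safety analysis the subject contributes nothing after Day 30. Whether data are lost then depends on something that happened during the implant, and the analysis plan has no step that would recover or correct for it.

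**Working it through.** **1. The rules side by side for this one subject**

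| Section | Rule turns on | Result for a removal followed by a second registry valve by MIS |
|---|---|---|
| 9.11.1 | Any removal before the index procedure ends | 30 days |
| 9.6.1 | Final result: no successful implant, or conversion | Not in the 30-day group (by implication) |
| 9.8.1 | Enrolment | 30 days and 6 months |
| 9.9 | A failed attempt, without saying any or final | Unclear |
| 12.1.2 | Registry valve in place on leaving, MIS | In the per protocol cohort |

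No section limits 9.11.1 to subjects left without a registry valve. Appendix C also defines implant failure as removal with the patient still in the operating room and does not mention a successful second valve. It attaches no follow-up rule to that term, but it makes the early-stop reading easier to reach.

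**2. What is not affected**

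The plan's only related figure is the power for cross-clamp time (12.5): above 90% with 300 registry subjects, 479 controls, a 15-minute difference, SD 16.0 and a two-sided 5% test.

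- SE = 16 × √(1/300 + 1/479) = 1.18 minutes.
- 15/1.18 − 1.96 = 10.8, so power is above 99.99%.

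The plan's statement reproduces. Cross-clamp time is measured during surgery, so this conflict cannot touch it. Technical success, first-attempt success and 30-day rates also stand.

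**3. What could be lost (illustration)**

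The documents give no second-attempt rate, so the share q is assumed at 1% to 10% of the maximum enrolment of 300. Late time per subject = (180 − 30)/365.25 = 0.411 years, and 300 × 0.411 = 123.2 late patient-years in all.

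For a 6-month event rate, assume p1 = 5% after a first-attempt implant and p2 = 5%, 10% or 20% after a second. With all subjects the rate is (1 − q)p1 + q·p2. Without the second-attempt subjects it is p1. The understatement is q(p2 − p1).

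| q | Subjects | Left at 6 months | Late patient-years lost | Understatement, p2 = 5% | p2 = 10% | p2 = 20% |
|---|---|---|---|---|---|---|
| 1% | 3 | 297 | 1.23 | 0 | 0.05 points | 0.15 points |
| 3% | 9 | 291 | 3.70 | 0 | 0.15 points | 0.45 points |
| 5% | 15 | 285 | 6.16 | 0 | 0.25 points | 0.75 points |
| 10% | 30 | 270 | 12.32 | 0 | 0.50 points | 1.50 points |

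For scale, the standard error of a 5% rate in 300 subjects is √(0.05 × 0.95/300) = 1.26 points. Up to a 5% share, the largest understatement is 0.75/1.26 = 0.6 standard errors. Six-month echocardiograms are collected only if available, so the real denominator for valve findings will probably be smaller and its standard error larger.

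**The case against.** The strongest reply is that the sections can be read together. Section 9.11.1 sits under the heading on valve explant, next to subjects who no longer have the valve, and can be taken to mean removal without re-implantation. It never says that the subject leaves the registry, whereas 9.6.1 and 9.11 say so when they mean it. The two 30-day exit reasons in 9.9 match the two scenarios in 9.6.1 one for one, so a failed attempt there most naturally means no successful implant. Section 12.1.2 defines an analysis set and sets no follow-up. The affected outputs are descriptive, and missing standard-of-care echocardiograms may well outweigh a handful of second-attempt subjects.

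Much of this stands. A reader might infer that the plan exits every subject whose first attempt failed, but the documents do not say that: 9.11.1 contains no exit, and 9.9 is best read with 9.6.1. A reader might also infer that second attempts are the technically difficult cases, so that the 6-month results would favor easy implants. Nothing in the documents gives reasons for second attempts or outcomes after them, and a change of valve size is equally possible.

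The reply does not remove the conflict. The reconciling reading of 9.11.1 has to be supplied by the reader, because the sentence as written covers every intra-operative removal. Section 9.9 does not say whether it means any attempt or the final one.

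**Conclusion.** The concern holds as a conflict of wording with a limited consequence. Section 9.11.1 prescribes 30-day follow-up for all intra-operative removals, while 9.6.1 goes by the final implant result and 9.8.1 calls for 6-month evaluation. A second-attempt MIS implant falls under both and stays in the per protocol cohort.

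If sites apply 9.11.1 literally, these subjects lack 6-month hemodynamics, NYHA class and quality of life. In the Kaplan-Meier and late linearized rates they are censored after Day 30; they are not deleted, and their early data still count.

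The size is unknown because no second-attempt rate is given, and it is probably small. The figures of 3 to 30 subjects and 0 to 1.5 points rest entirely on the assumed shares and event rates. If outcomes after a first and a second attempt are the same, the cost is some precision and no bias. The point is still worth settling, because 6-month data that are not collected cannot be recovered later.

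**What to change.** Reconcile 9.11.1 and 9.9 with 9.6.1 and 9.8.1, so that follow-up for this subject is stated once:

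- In 9.11.1, limit the 30-day follow-up to subjects who leave the operating room without a registry valve or who are converted to full sternotomy.
- State that subjects with a registry valve in place after a second MIS attempt continue to the planned 6-month visit.
- In 9.9, word the exit reason as no registry valve implanted after the final attempt.

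This follows the final-outcome logic already used in 9.6, 9.6.1 and 12.1.2. It concerns data collection at a visit already in the schedule and changes neither the sample size nor any analysis. The cost is a short amendment, a note to sites and a few more 6-month visits of the kind already planned.
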